#### 14.9 CLINICAL TRIAL RESULTS

The Sponsor will be responsible for preparing a clinical study report and to provide a summary of study results to the Investigator.

#### 14.10 PUBLICATIONS AND COMMUNICATIONS

Property of the Sanofi Group - strictly confidential

## 15 CLINICAL TRIAL PROTOCOL AMENDMENTS

All appendices attached hereto and referred to herein are made part of this clinical trial protocol.

The Investigator should not implement any deviation from, or changes of the clinical trial protocol without agreement by the Sponsor and prior review and documented approval/favorable opinion from the IRB/IEC of an amendment, except where necessary to eliminate an immediate hazard(s) to clinical trial patients, or when the change(s) involves only logistical or administrative aspects of the trial. Any change agreed upon will be recorded in writing, the written amendment will be signed by the Investigator and by the Sponsor and the signed amendment will be filed with this clinical trial protocol.

Any amendment to the clinical trial protocol requires written approval/favorable opinion by the IRB/IEC prior to its implementation, unless there are overriding safety reasons.

In some instances, an amendment may require a change to the informed consent form. The Investigator must receive an IRB/IEC approval/favorable opinion concerning the revised informed consent form prior to implementation of the change and patient signature should be re-collected if necessary.

# LIST OF ABBREVIATIONS AND DEFINITION OF TERMS

(No abbreviations defined yet)Ab: antibody

ADA: anti-drug antibodies/ anti-alirocumab antibodies

AE: adverse event

AESI: adverse event of special interest

ALP: alkaline phosphatase
ALT: alanine aminotransferase
ANCOVA: analysis of covariance
ANOVA: analysis of variance
Apo: apolipoprotein

ASCVD: atherosclerotic cardiovascular disease

AST: aspartate aminotransferase ATC: anatomic therapeutic chemical

BMI: body mass index

CBC: complete blood cell count CHD: coronary heart disease CI: confidence interval CKD: chronic kidney disease

CV: cardiovascular

DBP: diastolic blood pressure ECG: electrocardiogram

e-CRF: electronic case report form

eDISH: evaluation of drug-induced serious hepatotoxicity

eGFR: estimated glomerular filtration rate FDA: Food and Drug Administration

FPG: fasting plasma glucose
GFR: glomerular filtration rate
GGT: gamma-glutamyl transferase
GLP-1: glucagon-like peptide-1
HbA1c: glycated hemoglobin A1c

HCV: hepatitis C virus

HCV RNA: hepatitis C virus ribonucleic acid

HDL: high-density lipoprotein

HDL-C: high-density lipoprotein cholesterol

HLGT: high level group term

HLT: high level term

HR: heart rate

IDL: intermediate-density lipoprotein IMP: investigational medicinal product

ITT: intent-to-treat

IVRS: interactive voice response system IWRS: interactive web response system

LDH: lactate dehydrogenase

LDL: low-density lipoprotein

LDL-C: low-density lipoprotein cholesterol

LLOQ: lower limit of quantification

LLT: lowest level term

LMT: lipid modifying therapy

LOCF: last observation carried forward

Lp(a): lipoprotein a LS: least square

MAR: missing-at-random

MDRD: modification of diet in renal disease

MedDRA: medical dictionary for regulatory activities

MI: myocardial infarction

MMRM: mixed effect model with repeated measures

NMAR: not-missing-at-random NMR: nuclear magnetic resonance

non-HDL-C: non-high-density lipoprotein cholesterol

OLTP: open-label treatment period PAD: peripheral arterial disease

PCSA: potentially clinically significant abnormality PCSK9: proprotein convertase subtilisin kexin type 9

PT: preferred term
Q1: first quartile
Q2W: every 2 weeks
Q3: third quartile
QQ: quantile quantile
RBC: red blood cell

RDW: red blood cell distribution width

RNA: ribonucleic acid
SAE: serious adverse event
SBP: systolic blood pressure
SD: standard deviation
SE: standard error

SMQ: standardized MedDRA query

SOC: system organ class

TEAE: treatment-emergent adverse event

TG: triglyceride

TGRL: triglyceride rich lipoprotein TIA: transient ischemic attack

Total-C: total cholestorol

TSH: thyroid stimulating hormone ULN: upper limit of normal range ULOQ: upper limit of quantification VLDL: very low-density lipoprotein

WBC: white blood cell

WHO-DD: World Health Organization drug dictionary

# 1 OVERVIEW AND INVESTIGATIONAL PLAN

### 1.1 STUDY DESIGN AND RANDOMIZATION

This is a multicenter, multinational, randomized, open-label, parallel group stratified study.

After a screening phase of up to 3 weeks, patients will be centrally randomized via interactive voice response system (IVRS) or interactive web response system (IWRS) in a 2:1 ratio to one of the two treatment groups (alirocumab:usual care) and treated for 24 weeks.

Randomization will be stratified by the Investigator's selection of usual care therapy prior to randomization (5 strata: no additional lipid modifying therapy [LMT], or intent to prescribe fenofibrate, ezetimibe, omega-3 fatty acids, or nicotinic acid). Patients randomized to open-label alirocumab will continue on the maximum dose of statin that is tolerated by the patient and will administer alirocumab subcutaneously with a starting dose of 75 mg every 2 weeks for 12 weeks with a blinded up-titration to alirocumab 150 mg every 2 weeks at Week 12 visit if the non-high-density lipoprotein cholesterol (non-HDL-C) at the Week 8 visit is ≥100 mg/dL (2.59 mmol/L). Patients who have a non-HDL-C <100 mg/dL (2.59 mmol/L) at the Week 8 visit will continue with alirocumab 75 mg every 2 weeks until the end of the treatment period. Patients randomized to usual care will follow the option selected by the Investigator prior to randomization. No change during the course of the study will be made to the dose of LMT administered as part of the usual care arm except for nicotinic acid for which the Investigator may prescribe at randomization a scheduled/gradual dose titration in order to allow for the maximum dose to be achieved based on patient tolerability, or except if needed for any usual care LMT for the safety of the patient, based on the Investigator's judgment.

Approximately 420 patients will be recruited and randomized (280 in the alirocumab group and 140 in the usual care group).

# 1.2 OBJECTIVES

### 1.2.1 Primary objective

The primary objective of this study is:

• To demonstrate the superiority of alirocumab in comparison with usual care in the reduction of non-HDL-C after 24 weeks of treatment in patients with Type 2 diabetes and mixed dyslipidemia at high cardiovascular (CV) risk with non-HDL-C not adequately controlled with maximally tolerated statin therapy.

### 1.2.2 Secondary objectives

The secondary objectives of this study are:

Property of the Sanofi Group - strictly confidential

Page 7

26-Apr-2017

- 26-Apr-2017 Version number: Final
- To demonstrate whether alirocumab is superior in comparison with usual care in its effects on other lipid parameters at Weeks 12 and 24:
  - o low-density lipoprotein cholesterol (LDL-C)
  - o apolipoprotein B (Apo B)
  - o total cholesterol (Total-C)
  - o lipoprotein a (Lp(a))
  - o high-density lipoprotein cholesterol (HDL-C)
  - o triglycerides (TGs)
  - o triglyceride rich lipoproteins (TGRLs)
  - o apolipoprotein A-1 (Apo A-1)
  - o apolipoprotein C-III (Apo C-III)
  - o lipid subfractions by nuclear magnetic resonance (NMR) spectroscopy:
    - low-density lipoprotein (LDL) particle size
    - LDL particle number
    - very low-density lipoprotein (VLDL) particle number
    - high-density lipoprotein (HDL) particle number
    - intermediate-density lipoprotein (IDL) particle number
- To demonstrate the superiority of alirocumab in comparison with usual care in the reduction of non-HDL-C at Week 12
- To assess changes in diabetes related parameters in patients randomized to alirocumab versus usual care treatment over a period of 24 weeks
- To demonstrate the safety and tolerability of alirocumab
- To evaluate changes in proprotein convertase subtilisin kexin type 9 (PCSK9) concentrations at Weeks 12 and 24
- To evaluate the development of anti-alirocumab antibodies (ADA)
- To demonstrate the superiority of alirocumab versus fenofibrate therapy on non-HDL-C and other lipid parameters

### 1.3 DETERMINATION OF SAMPLE SIZE

[figure not shown]
#### 1.4 STUDY PLAN

This is a Phase 3b/4 randomized, open-label, parallel group study to assess the efficacy and safety of alirocumab administered by subcutaneous injection versus usual care in patients with Type 2 diabetes and mixed dyslipidemia at high CV risk with non-HDL-C not adequately controlled with maximally tolerated statin therapy. The study will be multinational and multicenter. The study consists of a screening period of up to 3 weeks, an open-label treatment period (OLTP) of 24 weeks, and a safety observation period of 8 weeks.

Patients, unless they are statin intolerant, will be taking a stable, maximally tolerated dose of statin therapy without other LMTs. Statin dose and dose regimen should be stable throughout the entire study duration including for 4 weeks prior to the screening period and from screening to the end of the OLTP. Patients should continue to follow a cholesterol lowering diet during the study, however, the Investigator may reinforce diet recommendations according to local/regional guidelines. Patients should be receiving treatment for diabetes in accordance with local/regional standards of care. Changes to antihyperglycemics should be limited and made only in circumstances where it is clinically needed.

The usual care arm includes the option to continue on the maximum dose of statin that is tolerated by the patient without the addition of a new LMT at randomization, or may initiate either ezetimibe, fenofibrate, omega-3 fatty acids, or nicotinic acid at randomization for the remainder of the 24-week treatment period. Initiation of usual care treatment should start as soon as possible after randomization, but no later than 7 days from the day of randomization.

The Investigator will select the most appropriate LMT for the patient prior to randomization (consisting of either no additional LMT but continuing on maximum tolerated statin, ezetimibe, fenofibrate, omega-3 fatty acids or nicotinic acid) and enter this information into the IVRS. If the patient is randomized to open-label alirocumab, the Investigator will not institute the LMT option that was selected and entered into IVRS but instead treat the patient with open-label alirocumab. If the patient is randomized to usual care (non-alirocumab), the Investigator will initiate treatment with the LMT option that was selected and entered into IVRS, as applicable, in addition to continuing the patient on the maximum tolerated dose of statin.

R: Randomization: As a principle, it should occur after signature of the informed consent form and just before the first dosing of the study drug (ie, IMP or usual care). The Randomization Day is always Day 1. The randomization is stratified by intent to precribe usual care (eg, intent to prescribe ezetimibe, intent to prescribe fenofibrate).

\*First study drug administration.

Phone call visits are indicated in italics.

#### 1.5 MODIFICATIONS TO THE STATISTICAL SECTION OF THE PROTOCOL

Not Applicable

# 1.6 STATISTICAL MODIFICATIONS MADE IN THE STATISTICAL ANALYSIS PLAN

Not Applicable

"Usual care includes continuing on maximum dose of statin tolerated by the patient (or no statin if statin intolerant) and one of the following: no additional LMT or initiation of either ezetimibe, fenofibrate, omega-3 fatty acids or nicotinic acid.

# 2 STATISTICAL AND ANALYTICAL PROCEDURES

### 2.1 ANALYSIS ENDPOINTS

The baseline value is defined generally as the last assessment obtained before the first injection of open-label alirocumab/first dose of usual care treatment or before randomization for patients randomized to usual care and not receiving additional LMT. All laboratory assessments taken the day of randomization will be considered as being performed prior to the first investigational medicinal product (IMP) administration.

All baseline safety and efficacy parameters (apart from those listed below) are presented along with the summary statistics in the safety and efficacy sections (Section 2.4.5 and Section 2.4.4).

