#### 9.1 PRIMARY ENDPOINT

# 9.1.1 Primary endpoint

The primary endpoint is the percent change in non-HDL-C from baseline to Week 24 in the intent-to-treat (ITT) population, using all non-HDL-C values regardless of adherence to treatment (ITT estimand).

The percent change is defined as:

100 x (non-HDL-C value at Week 24 – non-HDL-C value at baseline) / non-HDL-C value at baseline.

The baseline non-HDL-C value will be the last non-HDL-C level obtained before randomization for all patients. The non-HDL-C at Week 24 will be the non-HDL-C level obtained within the Week 24 analysis window.

All non-HDL-C values (scheduled or unscheduled, fasting or not fasting) between Weeks 8 to 24 may be used to provide a value for the primary endpoint, if appropriate, according to above definition.

The analysis window used to allocate a time point to a measurement will be defined in the statistical analysis plan (SAP).

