## 11.4.2.1 Analysis of primary endpoint

The percent change in non-HDL-C from baseline to Week 24 as defined in Section 9.1 will be analyzed in the ITT population using a Mixed-effect Model with Repeated Measures (MMRM) approach. All post-baseline data available within Week 8 to Week 24 analysis windows will be used and missing data are accounted for by the MMRM model.

The model will include the fixed categorical effects of treatment group (usual care versus alirocumab), the randomization stratum (as per IVRS), time point (Week 8, Week 12, Week 20 and Week 24), treatment-by-time point interaction, stratum-by-time interaction, as well as the continuous fixed covariates of baseline non-HDL-C value and baseline value-by-time point interaction. Model assumptions for normality will be explored prior to the analysis testing.

This model will be run using SAS Mixed procedure with an unstructured correlation matrix to model the within-patient errors. Parameters will be estimated using restricted maximum likelihood method with the Newton-Raphson algorithm. Denominator degrees of freedom will be estimated using Satterthwaite's approximation. This model will provide baseline adjusted LS means estimates at Week 24 for both treatment groups with their corresponding standard errors (SEs) and 97.5% confidence intervals (CIs). To compare the alirocumab group to the usual care group, an appropriate contrast statement will be used to test the differences of these estimates, at the 2-sided 0.025 level.

Let  $\mu 0$  and  $\mu 1$  be the population means of the percent change from baseline in non-HDL-C at Week 24 under usual care and alirocumab, respectively. The null hypothesis that will be tested is:

 $H0: \mu 0 = \mu 1$  versus $H1: \mu 0 \neq \mu 1$ 

Robustness of this statistical method will be assessed via sensitivity analyses detailed in the SAP, including different methodologies. In addition, a sensitivity analysis will be performed on the main analysis excluding non-HDL-C values assessed after the first treatment change compared to the randomized treatment (discontinuation or start of a new drug).

The same methodology will be applied to compare alirocumab versus fenofibrate in the "intent to prescribe fenofibrate" stratum.

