## 11.4.3 Analyses of safety data

The summary of safety results will be presented by treatment group. No formal inferential testing will be performed. Summaries will be descriptive in nature.

All safety analyses will be performed on the Safety population using the following common rules:

The baseline value is defined generally as the last available value before the first injection of open-label alirocumab/first dose of usual care treatment or before randomization for patient's randomized to usual care and not receiving additional LMT.

The following definitions will be applied to laboratory parameters and vital signs.

The potentially clinically significant abnormality (PCSA) values are defined as abnormal values considered medically important by the Sponsor according to predefined criteria/thresholds based on literature review and defined by the Sponsor for clinical laboratory tests and vital signs.

Potentially clinically significant abnormality criteria will determine which patients had at least 1 PCSA during the on-treatment period, taking into account all evaluations performed during the on-treatment period, including unscheduled or repeated evaluations. The number of all such patients will be the numerator for the on-treatment PCSA percentage.

The following definitions will be applied to AEs:

- Pre-treatment AEs are AEs that developed or worsened or became serious during the PRE-TREATMENT period
- Treatment-emergent AEs (TEAEs) are AEs that developed or worsened or became serious during the TEAE period
- Post-treatment AEs are AEs that developed or worsened or became serious during the POST-TREATMENT period

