### 2.1.3.1 Primary efficacy endpoint

The primary efficacy endpoint is the percent change in non-HDL-C from baseline (see definition of baseline in Section 2.1) to Week 24 in the intent-to-treat (ITT) population.

Non-HDL-C is defined as Total-C minus HDL-C.

The percent change is defined as: 100 x (non-HDL-C value at Week 24 - non-HDL-C value at baseline) / non-HDL-C value at baseline.

26-Apr-2017

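### Does it matter that the SAP ties baseline non-HDL-C to first dose while the protocol ties it to randomization?

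*SAP*

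**What the plan says.** Protocol 9.1.1 gives the primary endpoint its own baseline rule: "The baseline non-HDL-C value will be the last non-HDL-C level obtained before randomization for all patients". Protocol 11.4.2.1 adopts it by cross-reference: "The percent change in non-HDL-C from baseline to Week 24 as defined in Section 9.1 will be analyzed in the ITT population".

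SAP 2.1 has one rule for all parameters: "The baseline value is defined generally as the last assessment obtained before the first injection of open-label alirocumab/first dose of usual care treatment", with one exception, "or before randomization for patients randomized to usual care and not receiving additional LMT". It adds that laboratory samples from the day of randomization count as taken before first dose. SAP 2.1.3.1 applies this to the primary endpoint: "The primary efficacy endpoint is the percent change in non-HDL-C from baseline (see definition of baseline in Section 2.1) to Week 24". The same wording is in the protocol, but among the safety rules of Protocol 11.4.3: "The baseline value is defined generally as the last available value before the first injection of open-label alirocumab/first dose of usual care treatment".

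SAP 1.6, headed "STATISTICAL MODIFICATIONS MADE IN THE STATISTICAL ANALYSIS PLAN", is marked not applicable. So is SAP 1.5.

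**The concern.** Baseline non-HDL-C is the denominator of the primary percent change and a covariate in its model. Its definition should agree between the documents and should exist for every randomized patient.

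The SAP appears to have carried a safety convention into the primary endpoint without saying so. The departure also looks uneven by arm. Alirocumab is first injected at the randomization visit (Protocol 8.1.1.2), whereas a usual-care LMT may start up to 7 days later (Protocol 6.1, SAP 1.4). SAP 2.5.4 lets unscheduled values serve as baseline. A sample in that week would therefore be a baseline value under the SAP although it was taken after an open-label allocation was known.

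There is also a gap. SAP 2.2 counts an alirocumab patient as randomized whether or not the kit is used. A patient who is never injected has no first-injection date, yet SAP 2.3.1.1 requires a baseline for ITT membership. The fallback to the randomization day in SAP 2.5.2 covers adverse events only.

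**Working it through.** The plan gives no figure to reproduce here. The check is whether the two rules can pick different samples.

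**Interval in which they can differ** (after randomization, before first dose)
- Randomization is Day 1 (Protocol 1.1).
- Usual care with an added LMT: latest permitted start is Day 1 + 7 = Day 8, so the interval is Days 2 to 8.
- Usual care without an added LMT: none, because the SAP also uses randomization.
- Alirocumab injected at the randomization visit: none, because Day 1 samples count as pre-dose.

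**Scheduled lipid draws** (Protocol 1.2 and 10)
- Screening (Day -21 to -8), Day 1, Day 57 ±3, Day 85 ±3, Day 141 ±7, Day 169 ±3.
- Draws in Days 2 to 8: 0 of 6.
- Earliest Week 8 draw: 57 − 3 = Day 54, which is 54 − 8 = 46 days after the interval closes.

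**Order of events on Day 1**
- Protocol 10.1.2.1 lists the fasting sample before the IVRS randomization step, and SAP 2.1.4 states that samples are to precede randomization. The Week 0 value therefore satisfies both rules.

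**What could still put a sample in the interval**
- Protocol 6.1 discourages any independent lipid check after randomization before the Week 24 visit, except for patient safety, and keeps such results from the sponsor.
- Protocol 11.4.2.2 and SAP 2.4.4.2.4 exclude values from other laboratories.
- What remains is an off-schedule central-laboratory sample, for example a safety recheck or a Week 0 draw taken late and out of sequence, before the first LMT dose.

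**Size if it happened** (assumed values; the documents give none)
- Percent change = 100 × (Week 24 − baseline) / baseline.
- Baseline 150 mg/dL, Week 24 120 mg/dL: 100 × (120 − 150)/150 = −20.0%.
- Baseline 5% lower, 142.5: 100 × (120 − 142.5)/142.5 = −15.8%.
- Baseline 5% higher, 157.5: 100 × (120 − 157.5)/157.5 = −23.8%.
- One such patient among about 140 in usual care moves the unadjusted arm mean by about 4.2/140 = 0.03 percentage points in one direction, or 3.8/140 = 0.03 in the other.

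**Never-injected alirocumab patient**
- The first injection is supervised on site at the randomization visit. To matter, a patient must be randomized, miss that injection, never have another, and still return for a non-HDL-C sample. SAP 2.1 describes its rule as general, and SAP 2.5.3 counts study days from randomization for everyone. An analyst would take the Week 0 sample, as the protocol rule does.

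**The case for a change.** The best case for a change is one of principle. A primary-endpoint baseline should precede randomization, above all in an open-label trial. Describing the SAP rule as general does not rescue it, because SAP 2.1.3.1 cites it directly and offers no override. SAP 1.6 was the place to record the departure, and one sentence would restore the protocol's definition.

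The mismatch and the missing declaration stand. The SAP 1.5 entry is weaker evidence, since that section concerns the protocol's statistical section and the baseline rule sits in Section 9, reached only by cross-reference.

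The proposed repair brings no gain and has a drawback. Non-HDL-C is Total-C minus HDL-C, and triglyceride-rich lipoprotein cholesterol is non-HDL-C minus LDL-C (SAP 2.1.3.1 and 2.1.3.2.3). If non-HDL-C alone were tied to randomization, then in the one case where the rules differ its baseline would come from a different sample than the baselines of Total-C, HDL-C and LDL-C. Tying every lipid to randomization avoids that split but can cost data: Apo B, Lp(a) and the NMR measures have no screening sample (Protocol 10), so a late Week 0 draw would leave no baseline for them. The SAP's single rule keeps the lipids together, and any value it admits is still taken before treatment.

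**Conclusion.** No change is needed. The documents disagree in wording on the primary baseline and the SAP does not declare it, but following the SAP as written gives a sound analysis. Every patient who follows the schedule has the same baseline under either rule. The expected effect is negligible, and it is zero if no central-laboratory lipid sample falls between Day 1 and first dose and no alirocumab patient goes uninjected. No bias in either direction is shown. The uninjected patient is a wording gap with an obvious answer, the pre-randomization sample.

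This rests on usual-care LMTs starting within the permitted 7 days, alirocumab being injected at the randomization visit, and Week 0 samples preceding the IVRS step. The documents give no frequency for departures from these. It would take many off-schedule samples, concentrated in usual-care patients starting an LMT, before the choice of rule could be seen in the estimate.
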